#### HEMATOLOGY

#### Omadacycline (PTK 0796)

Paratek Pharma, LLC

#### PTK0796-AP-17202 Statistical Analysis Plan

		CHEMISTRY			
	Grade 0	Grade 1	Grade 2	Grade 3	Grade 4
Hyponatremia (mEq/L) (Na)	> 135	130-135	123-129	116-122	< 116
Hypernatremia (mEq/L) (Na)	< 146	146-150	151-157	158-165	> 165
Hypokalemia (mEq/L) (K)	> 3.4	3.0-3.4	2.5-2.9	2.0-2.4	< 2.0
Hyperkalemia (mEq/L) (K)	< 5.6	5.6-6.0	6.1-6.5	6.6-7.0	> 7.0
Hypoglycemia (mg/dL) (glucose)	≥65	55-64	40-54	30-39	< 30
Hyperglycemia (mg/dL) (nonfasting and regardless of prior history of diabetes)  (glucose)	< 116	116-160	161-250	251-500	> 500
Hypocalcemia (mg/dL) (corrected for albumin)  (Ca)	> 8.4	8.4-7.8	7.7-7.0	6.9-6.1	< 6.1
Hypercalcemia (mg/dL) (correct for albumin)  (Ca)	≤ 10.5	10.6-11.5	11.6-12.5	12.6-13.5	> 13.5
Hypomagnesemia (mEq/L) (Magnesium)	> 1.4	1.4- 1.2	1.1-0.9	0.8-0.6	< 0.6
Hypophosphatemia (mg/dL) (P)	≥ 2.5	2.0-2.4	1.5-1.9	1.0-1.4	< 1.0
Hyperbilirubinemia (total bilirubin)	< 1.1×ULN	1.1-1.5×ULN	> 1.5-2.5×ULN	> 2.5-5×ULN	> 5×ULN
Urea	< 1.25×ULN	1.25-2.5×ULN	> 2.5-5×ULN	> 5-10×ULN	>10×ULN
Hyperuricemia (uric acid) (mg/dL)	< 7.5	7.5–10.0	10.1–12.0	12.1–15.0	> 15.0
Creatinine	$< 1.1 \times ULN$	1.1-1.5×ULN	> 1.5-3.0×ULN	> 3.0-6×ULN	> 6×ULN

 The DMID toxicity table reports hyperglycemia detected in nonfasting specimens obtained from subjects with no prior diabetes.

 Calcium corrected for albumin = [0.8 x (normal albumin - subject's albumin)] + serum Ca level

Where normal albumin = 4 g/dl, albumin is in g/dL and calcium is in mg/dL

	ENZYMES					
	Grade 0	Grade 1	Grade 2	Grade 3	Grade 4	
AST (SGOT)	< 1.25×ULN	1.25-2.5×ULN	> 2.5-5×ULN	> 5-10×ULN	>10×ULN	
ALT (SGPT)	< 1.25×ULN	1.25-2.5×ULN	> 2.5-5×ULN	> 5-10×ULN	>10×ULN	
GGT	< 1.25×ULN	1.25-2.5×ULN	> 2.5-5×ULN	> 5-10×ULN	>10×ULN	
Alkaline Phosphatase	< 1.25×ULN	1.25-2.5×ULN	> 2.5-5×ULN	> 5-10×ULN	>10×ULN	
Amylase	< 1.1×ULN	1.1-1.5×ULN	> 1.5-2.0×ULN	> 2.0-5.0×ULN	> 5.0×ULN	
Lipase	$< 1.1 \times ULN$	1.1-1.5×ULN	> 1.5-2.0×ULN	> 2.0-5.0×ULN	> 5.0×ULN	

#### ENZVMES

Page 47 of 49

293 Version: 1.0 Status: Approved Approved Date: PTK0796-AP-17202 Statistical Analysis Plan

Omadacycline (PTK 0796)

Paratek Pharma, LLC

PTK0796-AP-17202 Statistical Analysis Plan

# APPENDIX 4 CONCOMITANT MEDICATION START DATE IMPUTATION

Parameter	Type of Medication	Imputation
Start date for con meds	Non- Antibacterial	If it cannot be determined whether or not the start date of a medication (non-antibacterial) is prior to the first dose of study drug, it will be assumed that the medication was received prior to the first dose of study drug.
	Antibacterial	Missing start dates for antibacterials will be queried for a value. If it cannot be determined whether or not the start date of an antibacterial is prior to the first dose of study drug, it will be assumed that the medication was received prior to the first dose of study drug unless the indication notes that the medication was received after the first dose of study drug.
Stop date for con meds	Non- Antibacterial	If it cannot be determined whether or not the stop date of a medication (nonantibacterial) is after the first dose of study drug, it will be assumed that the medication was received after the first dose of study drug
	Antibacterial	Missing stop dates for antibacterials will be queried for a value. If it cannot be determined whether or not the stop date of an antibacterial is after the first dose of study drug, it will be assumed that the medication was received after the first dose of study drug unless the indication notes that the medication was received prior to the first dose of study drug. If it cannot be determined whether the antibacterial was received prior to the assessment of Early Clinical Response, the EOT and/or the PTE Visit, the antibacterial will be assumed to have been received through the PTE Visit.

## **APPENDIX 4 ADVERSE EVENT START/STOP DATE IMPUTATION**

Parameter	Missing	Additional Conditions	Imputation
Start date		M and Y same as M and Y of first dose of test article	Date of first dose of test article
for AEs	D	M and/or Y not same as date of first dose of test article	First day of month
		Y same as Y of first dose of test article	Date of first dose of test article
	D and M	Y prior to Y of first dose of test article but same as Y of screening date	Date of screening date
	D, M, Y	None - date completely missing	Date of first dose of test article
Stop date		M and Y same as M and Y of last dose of test article	Date of last dose of test article
for AEs	D	M and/or Y not same as date of last dose of test article	Use last day of month
	DaniM	Y same as Y of last dose of test article	Date of last dose of test article
	D and M	Y not same as Y of last dose of test article	Use Dec 31
	D, M, Y	None - date completely missing	No imputation, but assume ongoing

D=day, M=month, Y=year

Page 48 of 49

93 Version: 1.0 Status: Approved Approved Date: PTK0796-AP-17202 Statistical Analysis Plan

Omadacycline (PTK 0796)

Paratek Pharma, LLC

PTK0796-AP-17202 Statistical Analysis Plan

Note: In all cases, if an estimated start date is after a complete stop date, use the first day of the stop date month. Similarly, if the estimated stop date is before a complete or imputed start date, use the last day of the start day month.

In all cases, if it cannot be determined if the adverse event occurred prior to or after the first dose of test article, the adverse event should be defined as treatment emergent.

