## 5.2 Definitions

In Table 2 general definitions are provided used in the statistical analysis.

Variable	Definition		
Baseline	Unless otherwise stated, baseline is defined as the value closest to but prior to the initiation of test article administration.		
Change from baseline	Change from baseline will be defined as the post-baseline value minus the baseline value (on a subject level). Change from baseline will only be calculated for subjects who have both baseline and at least one post-baseline value for any parameter.		
Duration Variables	Duration variables will be calculated using the general formula:		
	Duration (days) = End date - Start date + 1		
	If applicable, where time is collected:		
	Duration (hh:mm) = End datetime - Start datetime		
Calculated Creatinine Clearance (mL /min),	(140 – age [yrs]) * weight [kg] * Z	Z = 0.85 for Female subjects	
Cockcroft-Gault equation	Creatinine [mg/dL] * 72		
Body Mass Index (BMI)	$BMI = Weight (kg) / Height (m)^2$		

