# 5.3 Missing Data and Data Imputation Methods

Missing data will be handled as outlined below

- 1. Adverse Events and Safety Data:
- All missing and partial dates for AEs will be queried for a value. If no value can be obtained, substitutions will be made as detailed in Section 8.4. These substitutions will be used in calculations; however, the actual value recorded on the eCRF will be used in all listings.
- If the time of the first dose of test article is missing, it will be imputed with time of randomization + 1 minute. If time is missing for other doses it will be imputed with time of previous dose + 12 h.
- An AE is considered treatment emergent if the AE start date and time is on or after the start date and time of the first dose of test article.
- If time of the AE is missing and it occurred on the same date as the first dose of test article, the AE will be defined as treatment emergent. If the start date of the AE is partial or missing and it cannot be determined if the AE occurred prior to or after the first dose of test article, the AE should be defined as treatment emergent. Appendix 4 Adverse Event Start/Stop Date Imputation provides imputation for partial or missing date information. For AE listings, all dates and times will be displayed as reported on the Case Report Forms.
- If no value can be obtained for all other times for events and assessments occurring after randomization, the time will not be imputed but will remain missing.
- The severity and causality assessment for AEs cannot be missing. Missing data will be queried for a value. The highest severity and most related causality should be used if query is missing. If query will return missing, then the highest severity and most related causality will be used for the purpose of summaries.
- If the reported value of a clinical laboratory parameter cannot be used in a statistical summary table (e.g., a character string is reported for a parameter of the numerical type), a coded value must be appropriately determined and used in the statistical analyses. A value that is in the lower limit of the normal range will be calculated as 99.99% of the value if it is reported as "<" (e.g. <5 will be converted to 5\*0.99=4.9995). A value that is in the upper limit of the normal range will be converted to 100.01% if it is reported as ">" (e.g.>7 will be converted to 7\*1.001=7.007). However, the actual values as reported in the database will be presented in data listings.

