In addition, all AEs (including non-TEAEs), serious TEAEs, and TEAEs leading to discontinuation of test article will be provided in listings by treatment group, study site, subject, verbatim term, MedDRA SOC and PT, start and end date, seriousness flag, severity, relationship to test article, relationship to study protocol, action taken with test article, non-test article action taken and outcome.

For subjects with a TEAE of nausea or vomiting (based on the MedDRA PT), the total number of nausea and vomiting events, descriptive statistics of the study day of first onset of these events, and descriptive statistics for the duration (in days) of events, will be presented by treatment group.

Listings of hospitalizations will be provided.

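### The rules for partial AE stop dates are inconsistent: records one day apart in onset can get nausea durations of 1 and 21 days, and the imputed date ignores EOT and Final Follow-up

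*SAP*

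**What the plan says.** SAP 5.3 has missing and partial AE dates queried first. If the query yields nothing, a substitute date is used: "These substitutions will be used in calculations". Listings keep the recorded value.

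The substitutes for stop dates are in SAP Appendix 4, Adverse Event Start/Stop Date Imputation:

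- Day missing, "M and Y same as M and Y of last dose of test article": stop is the last-dose date.
- Day missing, "M and/or Y not same as date of last dose of test article": stop is the end of the reported month.
- Day and month missing, "Y same as Y of last dose of test article": stop is the last-dose date.
- Date wholly missing: "No imputation, but assume ongoing".
- Note below the table: "if the estimated stop date is before a complete or imputed start date, use the last day of the start day month".

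SAP 5.2 defines "Duration (days) = End date - Start date + 1". SAP 8.4 promises, for subjects with nausea or vomiting, "descriptive statistics for the duration (in days) of events" by treatment group.

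**The concern.** For a stop date in the last-dose month, the first rule picks the last day of dosing. The note, which applies as soon as onset falls after that day, picks the last day of the month. Two almost identical records can therefore be sent to dates weeks apart.

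No rule looks at what the visits showed. The EOT visit takes place 0 to 2 days after the last dose, so an event seen there can be given a stop date that precedes it. Month end has no upper limit tied to the subject's own follow-up. The order is also odd: a record with only the year known is closed at the last dose, while a record with nothing known stays open.

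The Protocol synopsis names nausea and vomiting as the AEs of interest, and Protocol 3.2 reports more of both than expected in the earlier cystitis study. Protocol 5.1 has daily visits on treatment, then EOT, then nothing until Day 21. An event that resolves in that gap is dated from recall, so some partial stop dates are plausible. If they occur, the duration summary would partly reflect the calendar instead of the drug.

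**Working it through.** The plan states no duration figure for this rule, so there is none to reproduce. The check applies the rule as written.

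**Inputs.** Stop-date rules: SAP Appendix 4. Duration = end − start + 1: SAP 5.2. EOT 0 to 2 days after last dose, and Final Follow-up on Day 28 ± 2 counted from first dose: SAP 3. Treatment for 7 to 10 days: SAP 3. The calendar dates are assumptions chosen for illustration.

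**1. Adjacent records.** Last dose 9 June, stop known only as June.

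- Onset 9 June: stop 9 June; 9 − 9 + 1 = 1 day.
- Onset 10 June: 9 June precedes onset, so stop 30 June; 30 − 10 + 1 = 21 days.

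**2. Other calendar dates.** Let the month have M days and the last dose fall on day d. Onset on day d gives d − d + 1 = 1 day. Onset on day d + 1 gives M − (d + 1) + 1 = M − d days. For d from 1 to M − 1:

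| Month length | Second record, range | Mean over d |
|---|---|---|
| 31 | 1 to 30 days | 15.5 |
| 30 | 1 to 29 days | 15.0 |
| 28 | 1 to 27 days | 14.0 |

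The gap between the two records is M − d − 1 days. It is 20 days in the example and zero at d = M − 1.

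**3. Conflict with EOT.** Onset 5 June, last dose 9 June, event still present at EOT, stop known only as June. The rule gives stop 9 June: 9 − 5 + 1 = 5 days.

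- EOT 9 June: true duration at least 5 days; no conflict.
- EOT 10 June: at least 6 days; the imputed stop is 1 day before the visit.
- EOT 11 June: at least 7 days; the imputed stop is 2 days before the visit.

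The longest duration compatible with a June stop is 30 − 5 + 1 = 26 days.

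**4. Month end against Final Follow-up.** Ten days of dosing ending 9 June put Day 1 on 31 May, Day 28 on 27 June, and the close of the + 2 day window on 29 June. Under the note, an event starting on 10 June gets stop 30 June, one day after the window closes. With 7 days of dosing ending 9 June, Day 1 is 3 June and Day 28 is 30 June, so there is no conflict at the nominal visit day.

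The different-month rule is also uncapped. Onset 29 May, last dose 30 May, stop known only as June gives stop 30 June: 3 days in May plus 30 in June = 33 days. With 7 to 10 days of dosing, Day 1 is 24 to 21 May, Day 28 is 20 to 17 June, and the window closes on 22 to 19 June. The imputed stop is 8 to 11 days later.

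**5. Under a single bounded rule.** Take the latest compatible date, capped at Final Follow-up. In the 10-day example with Final Follow-up on 27 June, onsets of 9 and 10 June give 27 − 9 + 1 = 19 and 27 − 10 + 1 = 18 days. With the 7-day course and Final Follow-up on 30 June they give 22 and 21 days. One day of onset now changes the duration by one day.

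**The case against.** The strongest defence is that this is a fallback convention with little reach. Partial dates are queried first, and Protocol 8.17 has investigators follow AEs until they subside or stabilise, so few stop dates may remain partial. The same rule applies in every arm of a blinded trial. Treatment emergence is decided by start date (SAP 5.3 and 8.4), so incidence tables do not change, and no efficacy result uses a stop date. All of this stands and limits the point to a minor one.

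Three further objections also stand in part:

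- The last-dose rule does not always shorten an event. Nausea that began on 5 June and resolved on 6 June lasted 2 days; the rule gives 5.
- Because Protocol 8.17 allows follow-up as medically necessary, a true stop after Final Follow-up is possible. The defect is that the rule reaches such a date without consulting the subject's record.
- Choosing the latest compatible date is itself a convention, and it leans long. Visit-level AE status is not among the listing fields in SAP 8.4, so a floor based on visits can apply only where that status was recorded.

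A reader might infer that events ongoing at EOT are generally ended too early. The documents do not support that. Wholly missing stop dates are left open, a stop in a different month goes to month end, and the conflict with EOT is at most 2 days and absent when EOT is on the last-dose day. A reader might also turn the 20-day gap into a shift in an arm's mean duration. That is not supported either: the frequency of such records is not given, and the gap compares two onsets under one rule, not the rule with the truth.

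**Conclusion.** The point holds for stop dates still partial after query. The rules contradict each other across a one-day difference in onset, giving 1 against 21 days in the example. The size ranges from no gap near month end to a second record of 30 days when the last dose is on the first of a 31-day month. The imputed stop can precede an EOT visit that saw the event by up to 2 days, and it can fall after the Final Follow-up window.

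The affected output is the descriptive duration summary for nausea and vomiting. No bias between arms is shown. The conclusion rests on the rule as written and on assumed calendar dates; how many records it touches is unknown. It is a minor defect, worth correcting because the correction is cheap.

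**What to change.** In SAP Appendix 4, replace the separate rules for partial AE stop dates with one: the latest date compatible with what was recorded, capped at the subject's Final Follow-up or last-contact date, and not earlier than onset or any visit at which the data show the event ongoing, where that is recorded. Leave wholly missing stop dates as they are. In SAP 8.4, add a repeat of the nausea and vomiting duration summary restricted to events with complete start and stop dates, so that the influence of imputation can be seen.

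The cost is a change of appendix wording, one extra table and a small programming change. The downside is that imputed durations will lean long; the complete-dates repeat shows by how much the summary depends on them.
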